## **6. STUDY DESIGN**

### **6.1 General study design and justification of design**

This trial is a randomized, controlled, double-blinded, placebo-controlled phase IIb/III trial investigating whether tranexamic acid is beneficial for the treatment of NOAC-ICH. Up to now, no evidence proven treatment for NOAC-ICH exists. The trial will be performed in 7 Swiss Stroke Centers recruiting 109 patients. Extension to international centers is intended.

### **6.2 Methods of minimising bias**

Patients recruited in this trial will be randomly allocated 1:1 to receive either tranexamic acid (TA) or placebo. Evaluation of the primary outcome parameter (HE) will be done by 3 independent raters blinded to study treatment.

#### **6.2.1 Randomisation**

Patients will be randomly allocated to TA or placebo in a 1:1 ratio. Randomisation will be performed by central computer over the Internet using the eCRF. The investigators will record patient details via a secure web interface before randomisation takes place. Investigators may also contact the Trial Coordinating Centre via the 24-hours help-line.

The randomisation procedure will include a standard minimisation algorithm which will ensure that the treatment groups are balanced for key prognostic factors, such as sex, age, NIHSS score on admission and use of specific antidote treatment. To avoid predictable alternation of treatment allocation, and thus potential loss of allocation concealment, patients will be allocated with a probability of 0.80 to the treatment group that would minimise the difference between the groups on the key prognostic factors.

## 7. STUDY POPULATION

Consecutive patients admitted to one of the participating stroke centers are enrolled according to the following inclusion and exclusion criteria:

### 7.1 Eligibility criteria

#### Inclusion criteria:

- Acute intracerebral haemorrhage
- Prior treatment with a non-vitamin K antagonist oral anticoagulant (NOAC: apixaban, dabigatran, edoxaban or rivaroxaban; last intake <48hours OR proven\* NOAC activity by relevant coagulation assays )
- Time of onset <12 hours (or in patients with unknown time of symptom onset, the time patient was last known to be well divided by 2)
- Age >18 years, No upper age limit
- Informed consent has been received in accordance to local ethics committee requirements

\*proven NOAC activity is defined as measurable NOAC plasma levels with a suitable specific coagulation test (calibrated anti-factor Xa activity, escarin clotting time) if available.

#### Exclusion criteria:

- Severe pre-morbid disability (modified Rankin scale >4)
- Anticoagulation with VKA
- Secondary intracerebral hemorrhage (e.g., AVM, tumor) Note it is not necessary for investigators to exclude underlying structural abnormality prior to enrolment, but where an underlying structural abnormality is already known, these patients should not be recruited.
- Glasgow coma scale <5
- pregnancy
- Planned neurosurgical hematoma evacuation within 24 hours (before follow-up imaging)
- Recent pulmonary embolism/deep vein thrombosis within the last 2 weeks

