### **4.3 Secondary Objectives**

Secondary objectives of this trial are to show that treatment with TA for NOAC-ICH increases the proportion of patients having a favourable clinical outcome and to show that TA influences hematoma expansion in different definitions.

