### **5.2 Secondary Outcomes**

Secondary outcome measures are

- (I) modified Rankin Scale (mRS) 0–4 at three-months;
- (II) mRS 0–3 at three-months;
- (III) Categorical shift in mRS at three-months;
- (IV) Absolute ICH growth volume by 24 ± 3 hours, adjusted for baseline ICH volume;
- (V) Symptomatic HE defined as HE and neurological deterioration of NIHSS >4 points or GCS >2 points
- (VI) Death due to any cause by three-months;
- (VII) major thromboembolic events (myocardial infarction, ischemic stroke, pulmonary embolism – safety endpoints)
- (VIII) NCH intervention (including craniectomy, EVD, hematoma evacuation)
- (IX) In-hospital mortality

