### 11.4 Planned Analyses

Analysis will be by intention-to-treat; Missing outcome data will be imputed assuming worst possible outcome.

The primary outcome (HE) is to be compared between treatment and control arms adjusted for baseline volume using binary logistic regression. Although both baseline covariate adjusted and unadjusted results will be reported, baseline covariate adjusted analysis is prespecified as the primary outcome analysis for this trial.

As secondary outcome analyses, the proportions of mRS 0–4, mRS 0–3, and mortality outcomes will be compared between active and placebo arms of the trial adjusted for baseline volume using a binary logistic regression model. Analysis of the categorical shift in mRS will also be undertaken on the full range of the mRS using the Cochran–Mantel–Haenszel shift test and proportional odds logistic regression, subject to the validity of shift analysis model assumptions. Other secondary outcome analyses will be carried out according to standard statistical principles for comparison of parametric or nonparametric distributions as appropriate.

Exploratory analysis will be run on the primary and secondary outcomes, with adjustments for baseline

variables such as age, Glasgow coma scale (GCS), presence of IVH, and ICH location, and in the following subgroups: onset-to-treatment time (<six vs. >six-hours), baseline ICH volume (<30 vs. >30 ml), anatomical location (deep, lobar, or cerebellar), IVH (absent vs. present), GCS (>12 vs. 8–12), and age (<70 vs. >70), presence of spot-sign. These analyses will be hypothesis generating, as the trial is not powered for them.

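### Premorbid mRS, which limits the three-month mRS and must be known for eligibility, is missing from the secondary mRS models, and patients with premorbid mRS 4 dilute the mRS 0–3 comparison

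*Combined protocol and SAP*

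**What the plan says.** The exclusion criteria in 7.1, and in the same terms the Study Synopsis, rule out "Severe pre-morbid disability (modified Rankin scale >4". Premorbid mRS 0 to 4 is therefore eligible.

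Section 4.3 sets the secondary aim of showing that tranexamic acid "increases the proportion of patients having a favourable clinical outcome". Section 5.2 lists three functional outcomes: "modified Rankin Scale (mRS) 0–4 at three-months", "mRS 0–3 at three-months" and "Categorical shift in mRS at three-months". None is defined relative to premorbid status.

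Under 11.4, the two binary mRS outcomes and mortality "will be compared between active and placebo arms of the trial adjusted for baseline volume using a binary logistic regression model". The shift analysis uses a Cochran–Mantel–Haenszel test and proportional odds regression, with no covariate or stratum named. Exploratory adjustment is for "variables such as age, Glasgow coma scale (GCS), presence of IVH, and ICH location". Premorbid mRS is not named there, among the subgroups, or among the minimisation factors in 6.2.1 (sex, age, NIHSS, antidote use).

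The Study Schedule and the flow chart in 9.1 both have an mRS entry at screening. The text does not say whether it is the premorbid or the acute score, and no analysis uses it. Section 11 promises a detailed analysis plan before the randomisation code is broken.

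**The concern.** Premorbid mRS is measured on the same scale as the outcome and in practice sets a ceiling on it. A patient at mRS 4 before the haemorrhage counts as a failure on mRS 0–3 whatever the treatment does, contributes nothing to the contrast, and pulls both arm rates towards zero. More generally, a patient's premorbid level is likely to predict the three-month level across the whole scale. Leaving it out of all three mRS analyses gives up power that could be had from a value the site must establish anyway to apply the exclusion criterion. At stake is the sensitivity of the functional outcomes that serve objective 4.3.

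**Working it through.** **The plan's own figure.** The only sample size is for haematoma expansion (11.2: 54% vs 27%, two-sided 0.05, 80% power). With mean rate 0.405, n per arm = [1.96·√(2·0.405·0.595) + 0.842·√(0.54·0.46 + 0.27·0.73)]² / 0.27² = 50.7, so 51 per arm and 102 in total. Dividing by 0.95 gives 108, close to the stated 109 (11.2 states the 5% loss only for the 218-patient case). The calculation does not involve mRS, and no power is stated for any mRS outcome.

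**Assumed inputs.** The documents give neither f nor any mRS 0–3 rate. I take f = 5–20%, and 40% vs 60% reaching mRS 0–3 among patients able to reach it.

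**Dilution.** If premorbid mRS 4 always fails, an arm rate p becomes p(1−f), and the difference is multiplied by (1−f). Unadjusted two-proportion power:

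| f | difference (points) | power, N = 109 | power, N = 218 |
|---|---|---|---|
| 0 | 20 | 55% | 85% |
| 5% | 19 | 51% | 81% |
| 10% | 18 | 47% | 77% |
| 15% | 17 | 43% | 72% |
| 20% | 16 | 40% | 68% |

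Example for f = 10%, N = 109: rates 0.36 and 0.54; z = [0.18 − 1.96·√(2·0.45·0.55/54.5)] / √((0.36·0.64 + 0.54·0.46)/54.5) = (0.180 − 0.187)/0.094 = −0.07, so power is 47%.

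**Chance imbalance in f.** Under simple randomisation with 54.5 per arm, the 95% range of the between-arm difference in f is ±1.96·√(2f(1−f)/54.5): ±8, ±11 and ±13 points at f = 5, 10 and 15%. If 45% of the other patients succeed, the mRS 0–3 difference moves by 0.45 times that, about ±4, ±5 and ±6 points. This lies inside the ordinary sampling error. At f = 10% the arm rate is 0.45·0.90 = 0.405, and the full 95% half-width is 1.96·√(2·0.405·0.595/54.5) = ±18.4 points. The imbalance component is (5.1/18.4)² = 8% of that variance. In simulations under no treatment effect, the volume-adjusted test without premorbid mRS rejected in about 4–6% of runs, and the test with it in 4.6–5.2%.

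**Gain from the covariate.** Logistic simulation of mRS 0–3, n = 109, 3,000 replicates, volume in the model, premorbid mRS 4 fixed at failure, slope −0.6 log-odds per premorbid point. Ranges cover different assumed premorbid distributions.

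| f | power without → with, log-OR 1.3 | power without → with, log-OR 0.8 |
|---|---|---|
| 5% | 74–76% → 80–82% | 38% → 44% |
| 10% | 67–70% → 77–79% | 33% → 41% |
| 15% | 62–64% → 74–77% | 30% → 37% |

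Across all runs the gain was roughly 5 to 10 points at log-OR 1.3 for f of 5–10%, 12 to 13 at f = 15%, and about 4 to 8 at log-OR 0.8.

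**Which mechanism produces it.** With the slope removed and only the mRS 4 block kept (log-OR 1.3), power went from 81.5% to 82.2% at f = 5% and from 75% to 78% at f = 10%. With no premorbid mRS 4 patients but the slope kept, the gain was about 3 points. Most of the gain therefore depends on premorbid mRS being prognostic across the scale.

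**The case against.** The case for leaving the plan alone is substantial.

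- **No bias.** A reader might infer that an unlucky split of premorbid mRS 4 patients would pass for a treatment effect. The documents do not support this. Allocation is randomised, the imbalance is part of the sampling variation that the confidence interval already covers, and type I error is nominal. Minimisation on age and NIHSS may offset some of it.
- **Narrow block.** A reader might also infer that objective 4.3 as a whole is undermined. The block affects only mRS 0–3. A premorbid mRS 4 patient meets mRS 0–4 by not worsening, and the shift analysis still uses movement across 4 to 6.
- **Optimistic simulation.** A log-OR of 1.3 is an odds ratio of 3.7, and neither it nor the slope comes from the documents. At log-OR 0.8 (odds ratio 2.2), power stays below 50% with or without the covariate.
- **Room in the plan.** The lists in 6.2.1 and 11.4 are illustrative, and a detailed analysis plan is still to come.

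The first three points stand and limit the size of the concern. The fourth stands only in part. The illustrative wording covers minimisation and exploratory adjustment, whereas the secondary binary models are specified with baseline volume alone. As written, they omit the covariate.

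**Conclusion.** The point holds as a matter of efficiency, not validity. The mRS 0–3 risk difference is diluted by (1−f), and all three mRS analyses forgo an available and probably strong covariate. The power gain from adding it is roughly 5 to 10 points at log-OR 1.3 for f of 5–10%, somewhat more at 15%, and about 4 to 8 at log-OR 0.8. It falls to about 0 to 3 points (f of 5–10%) if premorbid mRS matters only through the block at 4. All of this rests on an assumed f, slope and effect size. At f near 5% the dilution itself is small.

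The primary outcome and the sample size of 109 are unaffected, and nothing here shows that the eligibility limit is wrong. Minor priority.

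**What to change.** 1. In 11.4, add premorbid mRS next to baseline volume in the mRS 0–4, mRS 0–3 and proportional odds models. Enter it as a single ordered score: a separate category for premorbid mRS 4 would contain only failures on mRS 0–3 and could not be estimated.
2. In 9.1, state that the screening mRS is the premorbid score.
3. Report mRS 0–3 among patients with premorbid mRS 0–3 as a sensitivity analysis. This removes the dilution directly.

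Eligibility, primary outcome and sample size stay as they are. The cost is wording, settled before the code is broken, and one extra degree of freedom in secondary models. The odds ratios become conditional on premorbid mRS as well as on volume, which the report should say.

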### 7.2 Recruitment and screening

Patients will be recruited at the participating centers from the acute stroke unit or emergency department. Patients will be approached from a member of the patient's usual care team (which may include investigators). Local investigators or their nominee will inform the participant or their legal representative, of all aspects pertaining to participation in the study. It will be explained to the potential participant or their legal representative that entry into the trial is entirely voluntary and that their treatment and care will not be affected by their decision. It will also be explained that they can withdraw at any time but attempts will be made to avoid this occurrence. In the event of their withdrawal it will be explained that their data collected so far cannot be erased and we will seek consent to use the data in the final analyses where appropriate. If patients are unable to consent themselves (for example due to severe neurological deficits including impaired consciousness or aphasia) they can be included in the study if there is no information available (for example patient decree) providing evidence that the patient does not want to participate in any scientific study. In this case, an independent doctor unrelated to the study will ensure patient's custody. If the patients will be able to provide informed consent themselves at a later time point during the study, a signed informed consent from the patients will be obtained. If it is likely that the patient will not be able to give informed consent throughout the whole study period, a legal representative will be contacted to obtain informed consent as to the patient's presumed will.

### 7.3 Assignment to study groups

Patients will be randomly assign 1:1 one to receive either Tranexamic acid or placebo by a web-based randomization tool.

### 7.4 Criteria for withdrawal / discontinuation of participants

Participation in the trial is voluntary and patients are free to withdraw from the trial at any stage without

giving a reason. Study medication may be stopped at any time by the investigators or any treating clinician if deemed in the patient's best interest. Treatment (with tranexamic acid/placebo) will be given on top of 'best medical care'. Participants may be withdrawn from the trial either at their own request or at the discretion of the Investigator. The participants will be made aware that this will not affect their future care. Participants will be made aware (via the information sheet and consent form) that should they withdraw the data collected to date cannot be erased and may still be used in the final analysis. Enrolled participants who withdraw before randomisation can be replaced (though keeping their trial ID), but participants who withdraw after randomisation will not be replaced.

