## **5. STUDY OUTCOMES**

### **5.1 Primary Outcome**

The primary outcome measure is hematoma expansion (HE). In line with prior research, HE is defined as an increase of 33% relative or 6ml absolute growth between ICH-volume on baseline CT and on follow-up-CT at 24 ± 3 hours.

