## 9. STUDY ASSESSMENTS

Participants will be assessed before treatment (day 1), after treatment (day 2), after 7 days, at death/discharge and 90 days. See flow chart for more details.

Patients will be assessed clinically at baseline in line with local clinical practice prior to inclusion (day 1), end of treatment (day 2), on day 7 and at discharge/death (in hospital – if death/discharge occurs before day 7 visit, both visits are performed simultaneously). Follow up at day 90 (+/- 14 days) will be via a clinical outpatient visit or – if the patients' functional status does not allow outpatient visit – by a structured telephone interview with the patient, next-to-kin or other care-giver.

Brain imaging (CT head scan) will be performed as part of routine clinical management prior to enrolment (all acute stroke patients have a CT head scan performed on admission to hospital). For the purpose of the study the CT head scan will be repeated after treatment, day 2, (tranexamic acid/placebo) to assess haematoma expansion. A day 2 CT scan for patients with intracerebral haemorrhage is part of standard care in many stroke centers. In this case, routine day 2 CT scan can be used for trial purpose and no additional CT scan is required. If a patient received MRI scan on admission as first neuroimaging, the patient will undergo a baseline CT scan after inclusion in the trial to assure that hematoma expansion can be measured correctly and is comparable throughout all patients included in the study.

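### Section 7.4 allows discretionary investigator withdrawal from the whole trial and does not provide for outcome collection afterwards, so outcomes may go missing and be scored as worst

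*Combined protocol and SAP*

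**What the plan says.** Section 7.4 contains two distinct provisions.

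- On treatment: "Study medication may be stopped at any time by the investigators or any treating clinician if deemed in the patient's best interest".
- On participation: "Participants may be withdrawn from the trial either at their own request or at the discretion of the Investigator". No criteria are attached, and no request from the patient is needed.

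On data, 7.4 says that participants will be told that "should they withdraw the data collected to date cannot be erased and may still be used in the final analysis". On numbers, it says that "participants who withdraw after randomisation will not be replaced". Both clauses are worded for participants who withdraw; 7.4 has no separate text for those whom the investigator withdraws.

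Section 11.4 gives the analysis rule: "Analysis will be by intention-to-treat; Missing outcome data will be imputed assuming worst possible outcome". It makes no exception by reason for missingness, does not define the worst outcome for each endpoint, and names no sensitivity analysis for missing data.

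Section 5.1 fixes the primary outcome: "HE is defined as an increase of 33% relative or 6ml absolute growth between ICH-volume on baseline CT and on follow-up-CT", with the follow-up CT at 24 ± 3 hours. Section 9 says that where a follow-up CT is standard care, "routine day 2 CT scan can be used for trial purpose and no additional CT scan is required". It also allows the day 90 assessment by telephone, with the patient, next of kin or a care-giver.

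**The concern.** Treatment is one 10-minute loading infusion followed by one 8-hour infusion, and 7.4 already allows it to be stopped. What the second provision adds is a way out of the trial itself. The infusion period comes before the 24-hour CT, so a reaction or deterioration in those hours could lead to withdrawal before the primary outcome has been measured. Missing data of that kind depend on events after randomisation and may be related to outcome. They are also largely avoidable, because many of these patients will still be in hospital and the scan is already scheduled.

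The worst-outcome rule turns each such gap into an event. If the numbers are equal in the two arms, the difference is diluted. If they are unequal, the treatment effect is biased. Section 3.2.6 lists hypotension after rapid infusion, allergic skin reactions and thromboembolic events as known effects of TA, so unequal withdrawal is conceivable, although the documents do not put a size on it.

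**Working it through.** **Inputs.** HE 54% on placebo and 27% on TA, N = 109, two-sided 0.05, 80% power (section 11.2); allocation 1:1 (section 6.2.1), so 54.5 per arm. The 5% drop-out rate is stated in section 11.2 only for the 218-patient upper limit. Worst outcome is taken here to mean HE present. The test is the unadjusted two-proportion z-test with pooled null variance, not the planned logistic model adjusted for baseline volume.

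**Step 1: reproduce the plan's N.** The mean rate is (0.54 + 0.27)/2 = 0.405.

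n per arm = [1.96·√(2·0.405·0.595) + 0.842·√(0.54·0.46 + 0.27·0.73)]² / 0.27² = 50.7, so 51 per arm and 102 in total.

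102/0.95 = 107.4, so 108. The stated 109 is therefore close to 102 evaluable patients plus 5% simple loss. Section 11.2 does not say that 109 was built this way.

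**Step 2: effect of the imputation.** If a fraction w of an arm is missing and scored as HE, the observed rate is p* = p(1 − w) + w. At w = 0.05:

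- placebo: 0.54·0.95 + 0.05 = 0.563
- TA: 0.27·0.95 + 0.05 = 0.3065

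**Step 3: power.** Power = Φ[(d − 1.96·SE₀)/SE₁], where d is the difference, SE₀ the pooled standard error and SE₁ the unpooled one.

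| Scenario | Placebo vs TA | d | SE₀ | SE₁ | Power |
|---|---|---|---|---|---|
| Complete data, 54.5 per arm | 54.0% vs 27.0% | 0.270 | 0.0940 | 0.0904 | 82.8% |
| 5% simply lost, 51.8 per arm | 54.0% vs 27.0% | 0.270 | 0.0965 | 0.0928 | 80.8% |
| 5% in each arm scored as HE | 56.3% vs 30.7% | 0.257 | 0.0950 | 0.0917 | 77.9% |
| 5% in TA only scored as HE | 54.0% vs 30.7% | 0.234 | 0.0946 | 0.0920 | 69.9% |
| 5% in placebo only scored as HE | 56.3% vs 27.0% | 0.293 | 0.0944 | 0.0902 | 88.4% |

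**Step 4: range of assumed rates.**

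- Equal in both arms: 2% gives 80.9%, 10% gives 72.6%, 15% gives 67.3%.
- TA only: 2% gives 78.1%, 10% gives 54.5%.
- Placebo only: 10% raises the apparent benefit from 27.0 to 31.6 points.
- No true effect, 54% in both arms: 10% missing in one arm makes that arm's rate 0.54·0.90 + 0.10 = 0.586. This is a spurious difference of 4.6 points, and the rejection rate is about 7.7% instead of 5%.

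**Step 5: which outcomes are exposed.** Withdrawal before the 24-hour CT puts at risk the primary outcome and every later one. Withdrawal after the CT leaves the primary outcome intact and puts at risk only later outcomes, such as the day 90 mRS.

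**The case against.** The strongest reply is that the documents nowhere say that assessments stop. A reader might infer that 7.4 itself takes away the day 2 CT and the day 90 mRS; the text does not go that far. Data obtained before withdrawal may be used, so an event after the scan costs no primary outcome. A routine CT may exist, day 90 can be done by telephone, sections 9.2.3.1 and 10 follow deaths and vascular events beyond day 7, and section 7.2 undertakes to try to avoid withdrawal by patients. All of this stands, and it limits how often the problem would arise. It does not remove the problem, because none of these provisions is stated to apply to a patient who has been withdrawn.

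A second reply concerns size. The 5% is an all-cause figure, so attributing it wholly to investigator discretion is an assumption. Measured against a plan that probably allows for 5% loss, equal imputation costs about 3 points of power (80.8% to 77.9%), not 5. The one-arm scenarios need about three withdrawals in one arm before the CT (0.05 × 54.5 = 2.7) and none in the other. The trial is double-blind, the unblinded nurse is told not to disclose treatment and does not assess outcomes (section 8.1.4), and section 3.4 reports no excess thromboembolic risk over placebo in prior trials. This also stands: the one-arm figures show sensitivity and are not a forecast.

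A third reply is that the dilution and bias come from the worst-outcome rule, which also applies to missed scans and withdrawn consent. That is correct. The fix below reduces only the missing data that investigator discretion creates.

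**Conclusion.** The concern holds in a limited form. Investigator withdrawal has no criteria and is separate from stopping medication, the documents do not provide for later outcome collection, and any outcome that goes missing as a result would be scored as worst. If this accounted for the plan's full 5% drop-out equally in both arms, power at 109 would be about 78%, against about 81% with simple loss and 83% with complete data. Loss confined to one arm would shift the estimate towards or away from TA, depending on the arm. These figures rest on assumed rates, on worst outcome meaning HE present, and on an unadjusted test.

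Two stronger readings are not supported. The first is that power will fall to 70% or 55%: those values assume 5% or 10% loss in the TA arm alone, and the documents give no such rate. The second is that the intention-to-treat analysis is defeated: section 11.4 keeps every randomised patient in the analysis through imputation. What suffers is the share of outcomes that are observed and not imputed.

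This is a cheap improvement worth making, not a fatal flaw.

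**What to change.** Amend section 7.4 as follows.

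1. Investigator discretion applies to study medication only. The existing medication-stopping rule is left as it is.
2. All randomised patients, including those whose infusion was stopped, continue with the scheduled 24-hour CT, the day 2 and day 7 assessments, and the day 90 mRS and vital status.
3. Follow-up ends only when the patient or legal representative withdraws or refuses consent, or when evidence emerges that the patient did not want to take part. The last case is needed because sections 2.7 and 7.2 allow enrolment before consent has been obtained.
4. Where permitted, ask at that point whether routine scans and vital status may still be used.

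The cost is a short amendment to 7.4 and a note to sites. No new procedure is needed, because the scan and visits are already scheduled. The downside is slightly more follow-up work for patients who stop the infusion.
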